The protocol, informed consent form(s), recruitment materials, and all participant materials will be submitted to the Institutional Review Board (IRB) for review and approval. Approval of both the protocol and the consent form must be obtained before any participant is enrolled. Any amendment to the protocol will require review and approval by the IRB before the changes are implemented to the study. In addition, all changes to the consent form will be IRB-approved; a determination will be made regarding whether a new consent needs to be obtained from participants who provided consent, using a previously approved consent form.

1 STUDY SCHEME

2 INTRODUCTION

2.1 BACKGROUND AND RATIONALE

Non-specific effects (NSEs) of vaccines – also known as heterologous effects [1] – are those immune-mediated effects of vaccines on morbidity and mortality that are not explained by the prevention of the targeted disease [2]. Hypothetically, NSEs may be beneficial or detrimental. It has been proposed that this is determined by the type of vaccine [3], with NSEs of live vaccines (such as oral polio vaccine (OPV), Bacillus Calmette–Guérin (BCG) and measles-containing vaccines (MCV)) reducing all-cause mortality and NSEs of non-live vaccines (such as inactivated polio vaccine (IPV) and diphtheria tetanus and whole cell pertussis (DTP) combined vaccines) increasing all-cause mortality. It has also been reported that these NSEs on all-cause mortality are generally more pronounced in females than in males [4]. A systematic review of the evidence for NSEs of BCG, DTP and MCV on all-cause mortality in children under five years old provides support for these conclusions, although much of the evidence came from observational studies with a high risk of bias [5], and the importance and implications of these effects remain controversial [6]. There is a clear need for new data from randomised controlled trials (RCT), but there are logistic and ethical challenges to trials in children with relevant vaccines in high-mortality settings [6].

Recently, it was proposed that rabies vaccine (a non-live vaccine) has protective NSEs in people and in animals [7-9]. The higher number of cases of meningitis and of cerebral malaria among children receiving the RTS,S malaria vaccine than in controls who received rabies vaccine in a recent large RCT [10] can be explained by a protective NSE of rabies

vaccine [7, 8]. In a population-based cohort study, rabies vaccine was shown to be associated with decreased all-cause mortality in free-roaming dogs in a high-mortality setting [9]. A review of the literature revealed older studies in mice, using live attenuated rabies vaccine, that provided protection against *Klebsiella pneumonia* sepsis [11] and mortality following intracerebral injection of a neurotropic strain of herpes virus [12]. Studies have shown that part of the rabies virus (the nucleoprotein, which is present in the vaccine) acts as a non-specific immunological enhancer [13]. More recently, a controlled trial by the PI has shown that rabies vaccine reduces the risk of respiratory disease in feedlot cattle (manuscript in preparation). Further randomized controlled trials are needed to test for the effect in people.

A non-specific protective effect of rabies vaccine would have implications for prevention of rabies in endemic areas. In rabies-endemic areas, recognition of nonspecific effects of rabies vaccine in humans could affect public health decisions: Although rabies vaccine is known to be a safe and effective vaccine, its routine use as pre-exposure prophylaxis in children is not recommended as it is not cost-effective in most situations, in which the incidence of exposure to rabies is relatively low [14]. A substantial non-specific protective effect against other infections would improve the cost-comparability of routine pre-exposure prophylaxis vs. a reliance on post-exposure prophylaxis alone in areas where dog rabies is endemic. Post-exposure prophylaxis is not always affordable or readily available in many developing countries; hence incorporating rabies vaccine into routine childhood vaccination schedules could prevent rabies cases.

The aim of the proposed study is to determine if rabies vaccine reduces the incidence rate of episodes of common infectious disease syndromes in a population of veterinary students. The primary study endpoint will be a composite outcome of common infectious diseases (CID) including upper respiratory, diarrheal, and febrile illnesses. CIDs was chosen as the endpoints because of their common occurrence (and thus ability to have adequate study power), because of their public health and economic importance, and because no studies have yet documented rabies immunization effects on milder disease outcomes.

3 HYPOTHESIS, OBJECTIVES AND ENDPOINTS

3.1 PRIMARY HYPOTHESIS

Compared to an unvaccinated control group, administration of at least one dose of a three-dose course of rabies vaccine to previously-unvaccinated subjects leads to at least a 25% relative reduction in the rate of self-reported new episodes of common infectious disease syndromes (respiratory, diarrheal and febrile illness) over a 26-week period.

3.2 OBJECTIVES AND ENDPOINTS

3.2.1 PRIMARY

OBJECTIVES	ENDPOINTS	JUSTIFICATION FOR ENDPOINTS
To determine if the incidence rate of self-reported episodes of common infectious disease (CID) syndromes (respiratory, diarrheal and febrile illness) over a 26-week period is significantly different between previously-unvaccinated	Number of self-reported new episodes of acute common infectious disease (CID), defined as any of the following: upper respiratory illness (URI) or influenza-like illness (ILI) or diarrhea (DIA)	The assumption underlying the choice of a composite primary endpoint is that the biological mechanism that protects against infections that cause URI or ILI will also protect against infections that cause diarrhea or acute

OBJECTIVES	ENDPOINTS	JUSTIFICATION FOR ENDPOINTS

subjects that receive at least one dose of a three-dose course of rabies vaccine and those subjects that receive a placebo injection.
 
Primary analysis will be based on an intention-to-treat analysis.
	
or undifferentiated febrile illness (UFI).
 
URI is defined as (two or more of the following: runny or blocked nose/sneezing/sore throat/cough) and (absence of itchy or watery eyes).
 
ILI is defined as [fever (feeling feverish, or an axillary, oral or otic temperature of 100°F or higher)] and (cough or sore throat).
 
DIA is defined as three or more loose stools within a 24-hour period.
 
UFI is defined as [fever (feeling feverish, or an axillary, oral or otic temperature of 100°F or higher)] and (not meeting the case definition of URI, ILI or DIA).
 
To be defined as a new episode, illness must be preceded by at least one week without any CID.
 
Time Frame: Weekly self-reporting of occurrence or non-occurrence of episodes of CID for a maximum of 26 weeks, starting 10-14 days after allocation.
	
undifferentiated febrile illness, and therefore there is no need to separate those outcomes, and no biological basis currently for doing so. If rabies vaccine acts non-specifically to prevent some infectious diseases, its biological basis is unknown. However, the only existing data suggest it may work as a T-cell enhancer, which in theory could prevent any infectious disease.
 
Assessment of occurrence of study syndromes will be done on a weekly basis, through completion of a weekly survey of self-reported symptoms of illness by participants. For the composite outcome of CID, a week without any illness must occur before an illness is considered a new episode; a similar requirement will exist within individual disease syndromes.

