6.2 CONTROL GROUP

The intervention (placebo) in the control group is at least one dose (1 mL by intramuscular injection) of a three dose primary course (on days 0, 7 and 21) of vaccine diluent (sterile water for injection).

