6.3 DOSING AND ADMINISTRATION

Dosing and administration of the vaccine (Rabivax-S) will be according to the package insert, following the schedule for pre-exposure prophylaxis via the intramuscular route; that is, 1 mL by intramuscular injection in the deltoid area of the arm on Day 0, Day 7 and Day 21. Dosage and administration of the placebo (sterile water for injection) will follow the same schedule and route of administration; that is, 1 mL by intramuscular injection in the deltoid area of the arm on Day 0, Day 7 and Day 21. In the event of interruption of the schedule of administration (of either the vaccine or the placebo), the schedule will be

resumed without repeating a previous dose (as per Table 3 Recommendations for Interrupted or Delayed Routine Immunization – Summary of WHO Position Papers, updated April 2018; http://www.who.int/immunization/policy/immunization_tables/en/).

Vaccine and placebo will be administered to participants at the RUSVM Student Health Services by study nurses or nurse practitioner, using a 25G (0.50 x 25mm) needle and 2 mL syringe.

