7 PARTICIPANT TIMELINE

Students will be informed about the trial prior to the start of the semester for which they are eligible (orientation week for VP and 1st semester cohorts, and at the end of 4th semester for 5th semester cohorts). Students will be recruited into the study during orientation week and/or the first week of the semester, and will receive the first injection (day 0) within the first two weeks of the semester. Participants will receive the second injection on day 7 and the third injection on day 21. If necessary, participants can begin the intervention later, so long as day 0 falls within the first 12 weeks of the semester (see **Section 5.2.2, Exclusion criteria** for details).

Weekly illness surveys will begin in study week 3 (Monday of study week 3, day 10-14 after first injection) for all participants, and will continue for 26 weeks (through week 11 of the following semester in the case of a two-week semester break, or week 10 of the following semester in the case of a three-week semester break). One week after receipt of the final (26th) weekly survey, participants will be unmasked and will exit the study. Following exit, participants who were allocated to the control group will begin a primary course of rabies

vaccine in weeks 11 or 12 (depending on 3- or 2-week semester break), to be completed by the end of the semester (weeks 14 or 15).

A participant is considered to have completed the study one week after receipt of the final (26th) weekly survey.

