12 DATA COLLECTION METHODS

After enrollment, participants will complete a questionnaire that will capture data on relevant baseline characteristics including sex, age, health and vaccination status. (Baseline CRF; Appendix C). Participants will complete a short survey each week, starting in study week 3, to capture self-reported episodes of illness (respiratory, diarrheal and febrile illness; Primary Endpoint and Secondary Endpoints 1-5) in the preceding week (Appendix G). Surveys will be sent by email to all participants each Monday. Participants who have not completed the survey by Wednesday afternoon will be sent a request by email to complete the survey for the preceding week. Surveys will be sent weekly, for 26 weeks. A participant is considered to have completed the study one week after receipt of the final (26th) weekly survey for that participant's cohort.

As an incentive to enhance participant retention and response rates in weekly illness surveys, all participants who complete a weekly survey will be entered into a draw each week for a chance to win a EC\$25 gift voucher to a food/beverage vendor on the RUSVM campus. Selection of a winner each week will be done by computer-generated random sampling. The weekly winner will be notified by email in the week following the draw.

Clinically- and laboratory-confirmed episodes of study syndromes (Secondary Endpoints 6 & 7) will be collected by study personnel at RUSVM Student Health Services, as part of the

routine clinic visits and diagnostics. At the end of each 26-week observation period for each study cohort, data from that cohort will be compiled by the director of the RUSVM Student Health Services, anonymized to protect privacy and aggregated by study arm, before being sent to the Data Analyst who will conduct the analysis.

Occurrence of expected Adverse Events (Safety Endpoint 1) will be solicited in an online survey (Appendix H) sent to participants 3 days after receiving an injection (for dose 1, 2 and 3). Occurrence of unsolicited adverse events and serious adverse events (Safety Endpoint 2) will be captured by study personnel at RUSVM Student Health Services through completion of an Adverse Event form (Appendix I; See **Section 15.3, Identification of Adverse Events** for details).

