15.2 CLASSIFICATION OF ADVERSE EVENTS

All adverse events (AEs) will have their relationship to study intervention assessed by the Manager of the RUSVM Student Health Services (study nurse practitioner), in consultation with the study Medical Advisor, based on temporal relationship and clinical judgment.

The following guidelines will be used to describe severity:

- **Mild** – Events require minimal or no treatment and do not interfere with the participant's daily activities.
- **Moderate** – Events result in a low level of inconvenience or concern with the therapeutic measures. Moderate events may cause some interference with functioning.
- **Severe** – Events interrupt a participant's usual daily activity and may require systemic drug therapy or other treatment. Severe events are usually potentially life-

threatening or incapacitating. Of note, the term “severe” does not necessarily equate to “serious”.

The degree of certainty about causality will be graded using the categories below.

- **Related** – The AE is known to occur with the study intervention, there is a reasonable possibility that the study intervention caused the AE, or there is a temporal relationship between the study intervention and event. Reasonable possibility means that there is evidence to suggest a causal relationship between the study intervention and the AE.
- **Not Related** – There is not a reasonable possibility that the administration of the study intervention caused the event, there is no temporal relationship between the study intervention and event onset, or an alternate etiology has been established.

Adverse events will also be classified as **expected** or **unexpected**. An AE will be considered unexpected if the nature, severity, or frequency of the event is not consistent with the risk information previously described for the study intervention. Based on the information contained in the package insert for Rabivax-S, the following adverse events are considered expected:

- Local reactions (limited to the site of the injection): pain, erythema, oedema, pruritus and induration.
- Systemic reactions: fever, shivering, malaise, asthenia, faintness, dizziness, headache, myalgia, arthralgia, nausea and abdominal pain.

- Hypersensitivity or allergic reactions: anaphylaxis, urticaria, rash and erythema multiforme.

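### Vaccine-reaction fever after dose 3, and possibly dose 2, can count as a primary-endpoint illness; direct miscounting of a net excess biases the rate ratio upward, by an amount the protocol does not allow us to size

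*Combined protocol and SAP*

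**What the plan says.** **Endpoint (section 3.2.1).** The primary endpoint counts new episodes of common infectious disease (CID): upper respiratory illness (URI), influenza-like illness (ILI), diarrhea (DIA) or UFI. The UFI definition begins "UFI is defined as [fever (feeling feverish, or an axillary, oral or otic temperature of 100°F or higher" and applies when URI, ILI and DIA are not met. A new episode needs a CID-free week before it. Reporting runs "for a maximum of 26 weeks, starting 10-14 days after allocation".

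**Surveys.** Section 7: "Weekly illness surveys will begin in study week 3 (Monday of study week 3, day 10-14 after first injection". Section 12 says the survey captures illness for the "Primary Endpoint and Secondary Endpoints 1-5) in the preceding week (Appendix G".

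**Injections.** Section 6.3 gives both arms "1 mL by intramuscular injection in the deltoid area of the arm on Day 0, Day 7 and Day 21". The control arm receives injections "of vaccine diluent (sterile water for injection" (section 6.2).

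**Reactions.** Section 15.2 lists as expected "Systemic reactions: fever, shivering, malaise, asthenia" and others. Section 15.3 compares adverse event forms with the adverse event surveys to avoid double capture. It does not compare either with the weekly illness surveys.

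**Analysis.** Section 14 specifies an intention-to-treat analysis of all events and leaves further detail to a SAP. The hypothesis in section 3.1 is that vaccination "leads to at least a 25% relative reduction in the rate of self-reported new episodes".

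**The concern.** The composite is justified as a measure of protection against infection. A feverish day caused by the injection is not an infection, yet under the definition as written it can be counted as one. Because the comparator is sterile water, such reports may be more frequent in the vaccine arm.

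The primary hypothesis is a reduction. A net excess of counted fever-only episodes in the vaccine arm therefore works against it: power falls if the vaccine works, and the estimate tilts toward harm if it does not. The blinded sample size re-estimation in section 8 offers no protection. It re-estimates participation, control rate and dispersion, and cannot see a difference between arms.

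**Working it through.** **1. Timing.** Survey 1 is on the Monday at day 10-14 and asks about the week before. Survey 3 follows 14 days later.

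| Day 0 falls on | Survey 1 on day | Survey 1 recall (days) | Survey 3 recall (days) |
|---|---|---|---|
| Monday | 14 | 7-13 | 21-27 |
| Tuesday | 13 | 6-12 | 20-26 |
| Wednesday | 12 | 5-11 | 19-25 |
| Thursday | 11 | 4-10 | 18-24 |
| Friday | 10 | 3-9 | 17-23 |

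Day 21 (dose 3, on schedule) is in Survey 3's recall week in every row. Day 7 (dose 2) is in Survey 1's recall week in every row. Whether a Survey 1 illness can be a new episode is unclear: no earlier survey exists to show a CID-free week, and section 3.2.1 starts the time frame at day 10-14.

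**2. The plan's own figure.** Inputs from section 8: two-sided alpha 0.05, power 0.80, control rate 2, rate ratio (RR) 0.75, exposure 0.8, k = 0.4. Counted means are μc = 2 × 0.8 = 1.6 and μt = 1.6 × 0.75 = 1.2.

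- V = 1/μc + 1/μt + 2k = 0.625 + 0.833 + 0.8 = 2.258
- n per arm = (1.960 + 0.842)² × 2.258 / (ln 0.75)² = 214.2, so 215 per arm and 430 in total, as stated
- Power = Φ(−ln RR / √(V/215) − 1.96) = Φ(0.2877/0.1025 − 1.96) = 80.1%

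**3. Effect of an excess, dose 3 only.** Let p be the net (vaccine minus placebo) probability of a fever-only report after a dose. The documents do not give p; every value here is an assumption.

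*Unmasked upper bound:* μt = 1.2 + p, with every reaction counted. For p = 10%: μt = 1.30, RR = 1.30/1.6 = 0.8125, V = 0.625 + 0.769 + 0.8 = 2.194, power = Φ(0.2076/0.1010 − 1.96) = 54%.

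*Allowing for masking:* under the CID-free-week rule, a reaction adds nothing if the participant is already ill, and it can hide an illness in the following week. A weekly simulation used 600,000 participants per setting, gamma frailty with variance 0.4, and illness carrying into the next week with probability 0 or 0.3. It gave a net gain of 0.79-0.82 counted episodes per reaction week in Survey 3. Hence RR = (1.5 + gain × p)/2.0; for p = 10%, (1.5 + 0.079 to 0.082)/2.0 = 0.79.

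| Assumed p | RR, masked | Power, masked | RR, unmasked | Power, unmasked |
|---|---|---|---|---|
| 0 | 0.750 | 80% | 0.750 | 80% |
| 1% | 0.754 | 79% | 0.756 | 78% |
| 2% | 0.758 | 77% | 0.763 | 76% |
| 5% | 0.77 | about 73% | 0.781 | 68% |
| 10% | 0.79 | 64% | 0.813 | 54% |

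**4. Adding dose 2.**
- If Survey 1 can supply a new episode, the masked power for both doses at p = 1%, 2%, 5% and 10% is 77%, 74%, 63% and 43-44%.
- If it cannot, the values are 79%, 77%, 73% and 65%. A dose-2 reaction then can only hide a later episode. The net change is −0.06 episodes per reaction week, so at 10% RR falls by 0.06 × 0.10/2.0 = 0.003; a second simulation gave up to about 0.004.

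**5. No true effect, dose 3 only, p = 10%.** Unmasked, μt = 1.70 and RR = 1.06: significant harm 9.1% and significant benefit 0.5%, against 2.5% each nominally. Masked, RR = 1.04: 5.7% and 1.0%.

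**The case against.** **Size.** The case for leaving the plan alone is that materiality rests on a figure the documents do not contain. At 1-2% the loss is one to three points of power. Participants also have a separate day-3 survey that asks about fever, and some may report a reaction only there. This stands: the size cannot be set from the documents.

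**Existing safeguards.** Each syndrome is analysed separately (section 3.2.2), solicited events are compared by arm (section 3.2.4), and latency and dose effects are explored (section 3.2.3). These could reveal an excess. None of them corrects the primary estimate.

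**Stronger readings that a reader might infer, and that the documents do not support:**
- *The flaw could manufacture a protective result.* Direct miscounting of an excess runs the other way.
- *Every excess raises RR, and false protection is ruled out.* A dose-2 reaction that can only mask lowers RR negligibly. The direction statement also covers direct miscounting only. Self-report by participants who guess their arm from reactions is a separate route of unknown direction.
- *Power falls to about 43%.* That needs both p = 10% and a Survey 1 that can supply new episodes.
- *No exclusion rule exists.* Appendix G and the SAP were not available, and either could contain one.

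**Conclusion.** The point holds as a design weakness that should be fixed, with medium confidence. As written, the primary endpoint can count injection-related fever as infectious illness after dose 3, and after dose 2 if Survey 1 can supply a new episode. By direct miscounting, a net excess of counted fever-only episodes biases the rate ratio upward. The likely consequences are lost power or a tilt toward apparent harm.

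For dose 3 the loss is small at an assumed 1-2% net excess and material at 5-10%; nothing in the documents says which range applies. The figures also assume on-schedule dosing, the section 8 nuisance parameters, and missing surveys spread evenly over follow-up. If the SAP or Appendix G already contains a rule, section 3.2.1 need only refer to it.

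**What to change.** 1. In section 3.2.1, state which calendar days Survey 1 covers and whether Survey 1 can supply a new episode.
2. Before any by-arm fever data are seen, pre-specify one rule for both arms. A report that qualifies only as UFI, in a survey week containing an injection day or any of the 3 days after it, is not counted as a new CID episode and neither creates nor splits one. Take actual injection dates from the Visit 1-3 CRFs. Timing matters because sections 15.4 and 22 allow safety data to be reported or released before the main results.
3. Preferably make this the primary definition, with the all-reports definition as a sensitivity analysis. At minimum, make it a named sensitivity analysis of the primary endpoint.
4. Apply the same handling to Secondary Endpoints 1 and 5, to R50.9 visits in Endpoint 6, and to the first-event analyses, where an early reaction could become the first event.
5. Add a sensitivity analysis that treats ILI in those weeks the same way, since reaction fever with cough or sore throat is classed as ILI. Report affected weeks by arm.

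**Cost.** Endpoint wording, a few lines of derivation code and the extra analyses; the dates are already collected. Some genuine UFI episodes are lost. If UFI is 5-30% of episodes (an assumption) and 1-4 of 26 survey weeks are affected, the loss runs from 0.05 × 1/26 = 0.2% to 0.30 × 4/26 = 4.6% of episodes. At worst the means become 1.6 × 0.954 = 1.526 and 1.2 × 0.954 = 1.145, and power moves from 80.1% to 78.9%.
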